Secondary Endpoints: 1) Improvement in balance and fall risk as measured at baseline and 4 weeks. 2) 48 Hours of continuous daily physical activity using a validated body worn sensor as measured at baseline and 4 weeks. 3) Gait assessment at baseline and 4 weeks.

Specific Aim and Hypothesis

Aim 1. To assess the effectiveness of a micro-mobile foot compression device that provides mild compression to help reduce peripheral edema as compared to baseline in patients with both diabetes and lower extremity edema in a four-week observational clinical trial of 30 patients.

Hypothesis 1: The micro-mobile foot compression device will result in edema reduction when compared to baseline peripheral edema for the study population.

Aim 2. To assess the effect of micro-mobile foot compression device on the macro and micro lower extremity circulation as measured by Ankle Brachial Index (ABI) and Skin Perfusion Pressure (SPP) Measurements.

Hypothesis 2: The micro-mobile foot compression device will help improve macro and micro- circulation in the lower extremity of patients with diabetes and lower extremity edema as compared to baseline. We expect to see positive changes in ABI and SPP measurements.

Aim 3. To assess the effect micro-mobile foot compression device on the quality of life quantified using the validated, international quality of life assessment survey SF12, fear of falling quantified by FES-I, and risk of falling assessment quantified by gait, balance and spontaneous daily physical activity of patients with diabetes and lower extremity edema.

Hypothesis 3. The micro-mobile foot compression device will improve the quality of life, lower the risk of falling, lower fear of falling, and improve activity level of patients as compared to baseline assessments.

Section E: Protocol Risks/Subjects

E1. Risk Category

Category 2: Research involving greater than minimal risk, but presenting the prospect of direct benefit to the individual subjects.

E2. Subjects

Gender:

Both

Age:

Adult (18-64 yrs), Geriatric (65+ yrs)

Ethnicity:

All Ethnicities

Primary Language:

English, Spanish

Groups to be recruited will include:

Patients

Which if any of the following vulnerable populations will be recruited as subjects?

Vulnerable populations require special protections. How will you obtain informed consent, protect subject confidentiality, and prevent undue coercion?

E3. Pregnant woman/fetus

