Statistical Analysis - This study includes three hypotheses. To examine whether the proposed micro-mobile foot compression device will result in a edema reduction compared to the baseline (H1), we will use ANOVA and Fisher's exact tests for intra-subject rate of edema reduction using the outcome explained before. Multivariate and multiple linear regression test will be used for testing the effects of confounding factors including age, gender, BMI, foot insensitivity, etc. Additional, paired t-test will be used to examine whether amount of edema reduction at the end of study is significant compared to baseline. We will use Pearson correlation of coefficient and Fisher's exact tests to examine whether severity of neuropathy has any significant association with the rate of edema reduction. Finally, we will use multiple linear regression model to examine whether subject's level of activity, BMI, ABI, Skin perfusion pressure, and micro-mobile foot compression device are independent predictors for the rate of edema reduction.

To examine whether the proposed sock will help improve macro and micro-circulation in the lower extremity of patients (H2), we will use the similar analytical plan explained above by considering change in Skin perfusion pressure and ABI as dependent variables. For identifying the predictors, we will use multiple linear regression model and Anova (n-way). The independent variables will be severity of neuropathy quantified using Semmes Weinstein Monofilament, the level of activity, BMI, and age.

To examine whether the proposed socks will improve the activity level and quality of life (H3), we will use ANOVA multivariate test. The dependent variables will be number of total steps per day, duration of walking and standing, duration of longest episode of walking (i.e. continuous walking without stop), number of walking episode, duration of sit-to-stand and stand-to-sit postural transition, and SF12. We will use multiple linear regression model and multi-variant test to examine the effect of confounding parameters such as weather condition, BMI, age, etc.

Section H: Potential Risks/Discomforts

H1. Potential Risks/Discomforts

Describe and assess any potential risks/discomforts; (physical, psychological, social, legal, or other) and assess the likelihood and seriousness of such risks:

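### The H3 analysis lists no balance, gait or fear-of-falling variable, and its only effect test ignores direction, so it cannot by itself support the improvement H3 claims.

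*Combined protocol and SAP*

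**What the plan says.** Section D sets out three secondary endpoints: "1) Improvement in balance and fall risk as measured at baseline and 4 weeks"; "48 Hours of continuous daily physical activity using a validated body worn sensor as measured at baseline and 4 weeks"; and "3) Gait assessment at baseline and 4 weeks". Aim 3 adds SF12 and "fear of falling quantified by FES-I, and risk of falling assessment quantified by gait, balance and spontaneous daily physical activity". Hypothesis 3 is directional: the device "will improve the quality of life, lower the risk of falling, lower fear of falling, and improve activity level" relative to baseline.

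In Section G2 the H3 paragraph opens by restating the hypothesis as one about activity level and quality of life only. For that, "we will use ANOVA multivariate test". The outcomes follow: "The dependent variables will be number of total steps per day, duration of walking and standing, duration of longest episode of walking", then number of walking episodes, durations of the two postural transitions, and SF12. The rest of the paragraph covers confounders such as weather, BMI and age. The paired t-test in G2 is written for edema (H1). The H2 paragraph says it follows a similar plan; the H3 paragraph does not.

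**The concern.** There are two problems, one of coverage and one of fit.

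Coverage: Section D promises results on balance, gait and fear of falling, and Section F2 has patients complete balance stances under two eye conditions, several walking tasks and FES-I. Section G2 gives none of these an analysis. Each assessment yields many candidate variables (stance, eyes open or closed, velocity, stride measures, single or dual task). With none named in advance, a favourable one could be chosen after the data are seen.

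Fit: H3 claims improvement in each construct, but the only test of effect asks whether anything in the set changed, in any direction. A rejection is compatible with benefit, harm or a mixture. Section G1 also says the results will be used to calculate the sample size of a larger trial. That calculation needs a mean change and SD for each endpoint, which a joint test does not provide.

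**Working it through.** **1. Coverage.** The plan gives no figure to reproduce here, so I matched the endpoints in Section D to the H3 paragraph of G2.

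| Endpoint or construct (Section D) | In the G2 list for H3? |
|---|---|
| Balance (secondary endpoint 1) | No |
| Fall risk (secondary endpoint 1) | Indirectly, through activity-sensor measures |
| 48-hour activity (secondary endpoint 2) | Yes |
| Gait (secondary endpoint 3) | No |
| Fear of falling, FES-I (Aim 3) | No |
| SF12 (Aim 3) | Yes |

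The outcome list has no open ending, whereas the confounder list in the same paragraph ends in "etc.".

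**2. Direction.** The documents give no alpha, effect size, SD or correlation for H3. The following are therefore my assumptions: two-sided alpha 0.05; change scores with standardised mean change 0.5 and equal correlation r; and the multivariate ANOVA taken in its paired form, a one-sample Hotelling T² on baseline-to-4-week changes. I count p = 8 variables: steps, walking duration, standing duration, longest episode, number of episodes, sit-to-stand, stand-to-sit, SF12. The count is 6 if paired items are merged, and 9 if SF12 gives two summary scores. The documents give n as 30 (Section D) and 50 (Section G1), so I used both.

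Power comes from a noncentral F with p and n − p degrees of freedom and noncentrality λ = n·μ′R⁻¹μ, where μ is the vector of standardised changes and R their correlation matrix. Replacing μ by −μ leaves λ unchanged, so the test cannot tell improvement from worsening, whatever values are assumed.

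When all p changes equal ±0.5, λ = n·p·0.25 / (1 + (p − 1)r). With p = 8 and r = 0.5:

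- n = 30: λ = 30 × 8 × 0.25 / 4.5 = 13.33
- n = 50: λ = 50 × 8 × 0.25 / 4.5 = 22.22

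| True pattern | Power, n=30 | Power, n=50 |
|---|---|---|
| All 8 improve by 0.5 SD | 57% | 89% |
| All 8 worsen by 0.5 SD | 57% | 89% |
| Four improve, four worsen | about 100% | about 100% |

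A simulation of 10,000 trials at n = 30 gave 57.2% (all improve), 57.5% (all worsen) and 5.4% under no change. Across 6 to 9 variables and r from 0.3 to 0.5, the all-improve and all-worsen powers are equal in every case: 53% to 81% at n = 30 and 87% to 98% at n = 50.

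**3. Cost of per-endpoint tests.** For a paired t-test with a 0.5 SD change, the noncentrality is 0.5√n: 2.74 at n = 30 and 3.54 at n = 50.

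| Two-sided alpha | Power, n=30 | Power, n=50 |
|---|---|---|
| 0.05, unadjusted | 75% | 93% |
| 0.05/5 = 0.01, Holm's strictest step over five | 50% | 80% |

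**The case against.** The strongest reply concerns fall risk. Section F2 says the activity sensor also quantifies the risk of falling during daily living, and Aim 3 counts daily activity among its fall-risk measures. Since G2 analyses activity and postural transitions, fall risk is partly covered. That stands. A reader might infer that fall risk is wholly untested, and the documents do not support that. Balance, gait and FES-I still have no analysis.

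The second reply is that a multivariate ANOVA is normally read with its component means, and G2 does not forbid this. The wording is also loose, so Hotelling T² on eight changes is one reading of it. This has some force: the limitation belongs to the joint test, and component results would show direction. But G2 specifies no such results for H3, and if they were implied they would cover only the listed variables.

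Two stronger readings should not be drawn. A reader might infer that the joint test wastes power by diluting a gain on one outcome. With n = 30, 8 variables and a 0.5 SD gain on one of them, its power is 33%, 42%, 57% and 83% at correlations of 0, 0.3, 0.5 and 0.7, against 43% for a Bonferroni-corrected paired t-test. The ranking depends on a correlation that the documents do not give, and most of the variables come from one sensor recording, so zero correlation is unlikely. A reader might also infer that a patient missing one component is dropped from the whole analysis. That is a common software default; the plan states no such rule.

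Finally, this is a proof-of-concept pilot and these are secondary outcomes. That limits the stakes and makes formal multiplicity control optional. It does not remove the need for a per-endpoint estimate, because the pilot's stated use is to size a later trial.

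**Conclusion.** The point holds. Balance, gait and FES-I are named as endpoints or Aim 3 measures and have no analysis anywhere in the plan; of the three secondary endpoints, only activity is fully matched to the H3 list. This rests on the text alone.

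The only H3 effect test is blind to direction, so a significant result does not by itself support the improvement that H3 claims. The sign-blindness is exact for the joint test; the 57% and 89% figures illustrate it under the assumed 8 variables, correlation 0.5 and 0.5 SD change. The consequence is confined to the secondary aims, and the edema analysis is unaffected. This is a cheap improvement that should be made.

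**What to change.** In the H3 paragraph of Section G2:

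1. Replace the multivariate test as the effect analysis with the paired baseline-to-4-week mean change, its SD and a 95% CI for each H3 endpoint.
2. Add one named balance measure, one named gait measure and FES-I to the outcome list.
3. Either label these analyses exploratory, or choose one key outcome for each of five constructs (activity, balance, gait, fear of falling, SF12), apply Holm across them and report the rest descriptively.

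The change affects analysis wording only, because the assessments are already scheduled at baseline and 4 weeks. If Holm is chosen, the price is power: at its strictest step, about 50% at n=30 and 80% at n=50 for an assumed 0.5 SD change. The exploratory label avoids that price, and for a pilot it is sufficient.

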Diabetic foot ulceration (DFU) is a common and largely preventable complication. [1] While most of these ulcers can be treated successfully, some will persist and become infected. Ultimately, nearly one fifth of patients with infected lower-extremity diabetic ulcers will require amputation of the affected limb, resulting in staggering costs for both the patient and the healthcare system. Prevention by identifying people at higher risk is the key for better clinical management of such patients. It is not uncommon for patients suffering from diabetes to have concomitant lower extremity edema or even venous insufficiency[2-4] and they subsequently may benefit from graduated compression[5-7]. However, because of the common association of peripheral arterial disease (PAD) in patients with diabetes[8-10], most clinicians are reluctant to apply compressive dressings in fear of exacerbating the symptoms of PAD and the possible resulting gangrene[11].

Unfortunately, this area has received comparatively little attention from industry, academia, or insurance providers. A novel micro-mobile intermittent pneumatic foot compression device (AVEX Footbeat, Inc.) offers alternative means providing lower extremity compression. This device is portable and can be used in ambulatory settings providing increased venous blood and relief from concomitant lower extremity edema.

Section D: Purpose and Objectives

The purpose of this study is to conduct an observational study with N=30 patients to assess whether this micro-mobile foot compression device can help reduce lower extremity in patients with both diabetes and lower extremity edema without compromising the vascular supply.

The main purpose of this study is to determine if the device lessens edema. This study will also evaluate a new research device to see if it may help prevent diabetic foot ulcers. Additionally, it may potentially help delay progression of foot disease and produce a better quality of life by providing a better blood flow to foot and ankle.

Primary Endpoints: Reduction in lower extremity edema at 4 weeks of continuous device usage. Peripheral edema will be measured at baseline, 48 hours, 1 week and 4 weeks. Peripheral edema will be directly measured by traditional volume change assessment and indirectly by skin perfusion pressure assessment.

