Will pregnant women and/or fetuses (as described in 45 CFR 46 Subpart B) be enrolled in the research?

No

E4. Neonates

Will neonates of uncertain viability or nonviable neonates (as described in 45 CFR 46 Subpart B) be enrolled in the research?

No

E5. Children

Will children be enrolled in the research?

No

Section F: Design/Procedure

F1. Design

Select one category that most adequately describes your research:

c) Pilot

Discuss the research design including but not limited to such issues as: probability of group assignment, potential for subject to be randomized to placebo group, use of control subjects, etc.

In this proof of concept, intent to treat trial, 30 consecutive patients with diabetes and lower extremity edema will be recruited from the outpatient clinic at Baylor College of Medicine. Patients will be consented per the local Institutional Review Board's guidelines and approval for this study.

Inclusion Criteria:

a) Males or females age 18-90 years old with history of type 1 or 2 diabetes and the ability and willingness to provide Informed consent b) Patients at risk of developing diabetic foot ulcers c) Patient is willing to participate in all procedures and follow up evaluations necessary to complete the study. d) Patients who have undergone lower extremity surgery / amputation may be enrolled into the study at the clinical judgment of the Investigator

Exclusion Criteria:

a) Patients with severe peripheral vascular disease (ABI or ankle brachial systolic pressure index <0.5) b) Patients with diabetic foot ulcers in the plantar foot region c) Patients with active wound infection, or untreated osteomyelitis d) Patients currently on immunosuppressive drugs. e) Pregnant or breastfeeding females. (standard urine pregnancy done on women during physical exam procedures) f) Acute fractures of the foot g) Acute heart failure h) Participation in an interventional Study within the last 30 days i) Non-ambulatory or unable to stand without help or walk a distance of at least 6 feet without assistance. k) Patients with major foot amputation. j) Patients who are unable or unwilling to participate in all procedures and follow up evaluations h) Patients with major foot deformities which won't fit in the diabetic shoes

F2. Procedure

Following is a summary of study procedures:

Study Day 0 (initiation), Visit 1 The following baseline values will be assessed and documented.

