Screening/ Baseline: Subjects will be screened to ensure that they meet the inclusion criteria of the study. The study will be fully explained and written informed consent will be obtained from each patient prior to the initiation of screening procedures.

Cognitive assessment: The Montreal Cognitive Assessment (MOCA) is a series of questions used to assess cognitive status. A score less than 26 could indicate cognitive impairment. Although it is not an exclusion criteria, a score less than 26 will require PCP permission. Written permission from the patient will be asked for in order to contact their PCP for approval to participate in the study.

Physical exam: Physical exam will be conducted, including vascular, dermatological, and neurological, as part of a regular care visit.

Medical History: A detailed medical history will include: previous medical history, location and duration of previous ulcers, amputation (toe, foot, below knee, above knee), lower extremity bypass, lower extremity angioplasty, CABG, cardiac angioplasty, last visit by physician (in weeks), and current/past use of special shoes or insoles.

Neurological Evaluation: The Neurological assessment will consist of Vibratory Perception Threshold testing (VPT) using the technique described by Young [12], and the 10 gram Semmes-Weinstein monofilament using the criteria described by Armstrong and Lavery[13]. The presence of sensory neuropathy will be identified as vibratory perception threshold greater than 25 volts or inability to accurately perceive a 10 gram Semmes-Weinstein monofilament at 1 or more of 10 test sites on the sole and dorsum of the foot[14], which is a standard clinical measurement in diabetic patients.

Vascular Assessment: The vascular assessment will consist of palpation of the dorsalis pedis and posterior tibial arteries and non-invasive Doppler studies. Ankle Brachial Index (ABI) will be determined for both extremities [14, 15]. ABI ratios less than 0.5 will indicate severe vascular disease. These patients will be eliminated from the study per exclusion criteria.

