Additionally, skin perfusion pressure (SPP) monitor will be used to assess vascular status for all patients. SPP offers a non-invasive and real-time assessment of critical limb ischemia. It indicates the pressure at which blood flow resumes in capillaries. SPP is unaffected by falsely elevated systolic blood pressures, calcified arteries and peripheral edema. Typically SPP readings are obtained by photoplethysmography (cuff occlusion and re-appearance of pulsatile blood flux) or laser Doppler (cuff occlusion/thermal hyperemia and movement of red blood cells).

Edema Assessment – Peripheral edema will be assessed at baseline, using clinical signs and circumference measurements at foot, calf and ankles or via volumetric water displacement.

Physical Performance Tests - Balance assessment: Balance will be quantified using validated body worn sensors (BalanSens™, Biosensics LLC, USA). The system measures ankle and hip motion in three dimensions (3D), 2D COM sway as well as RCI in ML and AP directions [16]. Balance will be assessed according to Romberg protocol during eyes-open and eyes-closed condition during double, semi-tandem, and full tandem stances (see the attached list of questionnaires/assessments for further explanation).

Physical Performance Tests - Gait assessment: Gait performance will be assessed using by a validated body worn sensors (LegSys™, Biosensics LLC, USA) [17-19]. The device uses five sensor modules respectively attached to right and left anterior shins, right and left anterior thighs, and posteriorly to the lower back. Based on the subject's height and using a two-link inverse pendulum model the following spatio-temporal gait parameters will be estimated: velocity, stride length, stride time, double support, single support, stride-to-stride variability, and gait initiation [20]. In addition, the COM range of motion during walking will be calculated by using the data from the sensor attached to lower-back. Gait will be assessed over a distance of 20 meters under 4 conditions: (1) walking at habitual speed (single task); (2) walking at habitual speed while counting backward from a random number (e.g. 83) (dual task); (3) walking at maximum speed (fast walking), (4) Timed Up and Go (TUG); and (5) alternative 8 step test

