Upper Extremity Test: Investigators will measure arm motion from each participant by implementing a validated technology based on wearable sensor system named LegSys. This system will assess respectively spatio-temporal parameters of arm motion in a clinical setting. The LegSys system will be used with 2 sensors to capture arm motion, one placed at the subject's wrist and another at their elbow. While being at a comfortable position, the subject will be asked to flex and extend their arm for 20 seconds at a fast speed. Subject will also be asked to repeat this task but counting backwards as they flex and extend their arm (dual task). We may also add wrist weights (no more than 5 pounds) to increase the resistance of this task.

Objective assessment of physical activity: Spontaneous daily physical activities as well as the risk of falling during activity of daily living are quantified using a validated body worn sensor named PAMSys™ (Biosensics, LLC, USA). PAMSys is a small long-term recording movement sensor which is unobtrusively inserted into a comfortable shirt (PAMshirt™). The system contains inertial sensors with software developed to identify postural positions and movements such as walking, standing, sitting, or lying during a measuring period of 48 hr. It has proven to be sensitive (87–99%) and specific (87–99.7%)[21, 22] for postural position and detection of walking in different samples of older adults and patient groups.

Plantar Pressure Assessment: Plantar pressure will be examined using computerized pressure insoles® (Fscan®, TekScan, Boston, MA). Subjects will be asked to walk a distance of approximately 20 feet at habitual speed while wearing regular shoes with and without AVEX insoles.

Assessment of user friendliness, acceptability, and perception of need: We will use a questionnaire tailored to the topic of this study to evaluate the perception of the target population in receiving benefit from the proposed technology. Subjects are asked to answer the questionnaire at the end of study. The questionnaire includes 11 items and allows assessing how target population perceives the need of such technology in management of their problem.

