The AVEX Footbeat insole is an investigational device, which has been designed to enhance blood flow to lower extremities via a Micro-Mobile Foot Compression Device. The compression component applied pressure under your foot arch. We will perform initial screening to ensure the safety of the device. But as any new insole, there is some risk that the insole caused some discomfort or cause development of foot ulcers. It is important to notify us if you feel discomfort on wearing the insoles or if you feel excessive pressure to your feet because of wearing the AVEX Footbeat insole.

The study device and technology is completely non-invasive, safe, non-toxic and non-ionizing. The potential risks to you are minimal. However, like any battery powered systems, there is a minimum risk of sensor malfunctioning. In addition, the study devices are not waterproof, and although they use a low powered battery (similar to a cell-phone battery), in order to avoid any risk of shock the monitor should not be submerged or saturated with fluids during operations or cleaning.

You must be willing to charge device battery daily. Otherwise they will not receive benefit from compression component during treatment.

The assessments described above are expected to be minimal risk and probability and magnitude of harm or discomfort anticipated in the research are not greater in and of themselves than those ordinarily encountered in daily life or during the performance of routine physical or psychological examinations or tests.

Please note that there is also the possibility for loss of confidentiality. The PI and the research team will minimize the possibility of for loss of confidentiality by keeping all the physical data locked in cabinets only accessible to the research team. The electronic data will be kept on network password protected institutional computers. And, subject PHI will be coded as much as possible to minimize the potential for loss of confidentiality.

H2. Data and safety monitoring plan

Do the study activities impart greater than minimal risk to subjects?

No

H3. Coordination of information among sites for multi-site research

Is the BCM Principal Investigator acting as the SPONSOR-INVESTIGATOR for this multi-site research?

No or Not Applicable

Is BCM the COORDINATING CENTER for this multi-site research?

No or Not Applicable

Section I: Potential Benefits

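### H1 names foot ulcers as a risk of the insole, but each reporting trigger it states depends on sensation, in a trial that expects sensory neuropathy and does not exclude it

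*Combined protocol and SAP*

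**What the plan says.** H1 describes an insole that presses under the arch and says that "there is some risk that the insole caused some discomfort or cause development of foot ulcers". The instruction to participants that follows is "It is important to notify us if you feel discomfort on wearing the insoles or if you feel excessive pressure to your feet".

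F1 includes "Patients at risk of developing diabetic foot ulcers". It excludes "Patients with diabetic foot ulcers in the plantar foot region", an ABI below 0.5, and major deformities that the shoes cannot accommodate. Sensory neuropathy is not on the exclusion list. F2 (Neurological Evaluation) identifies it by a vibration threshold above 25 volts or "inability to accurately perceive a 10 gram Semmes-Weinstein monofilament at 1 or more of 10 test sites", and attaches no extra precaution to a positive finding. G2 treats foot insensitivity as a confounder and tests neuropathy severity against edema change.

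Several safeguards are stated:
- Visit 1 includes a physical exam with a dermatological part, a shoe-fit test, and plantar pressure measured "while wearing regular shoes with and without AVEX insoles".
- Adverse events are assessed at Visit 2 (48 hours) and Visit 3 (1 week). At Visit 3, repeating the Visit 1 assessments is optional.
- Section D says "Peripheral edema will be measured at baseline, 48 hours, 1 week and 4 weeks". The baseline method in F2 is clinical signs and "circumference measurements at foot, calf and ankles or via volumetric water displacement".
- Visit 4 (4 weeks) is to have assessments similar to those of Day 0.
- Photographs and thermal images are planned to follow any worsening; they are not tied to a visit.

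**The concern.** Loss of protective sensation means that an injury to the foot may not be felt. H1 foresees one specific tissue injury, and the warning signs it gives are the ones that a person with neuropathy is least able to notice. The instruction therefore works least well for the participants who most need it.

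At stake is time to detection. A participant who cannot feel the loaded area may have redness, a blister or a skin break with no symptom that matches the instruction. That participant could keep using the insole over a lesion that a look at the foot would have shown. The primary endpoint assumes four weeks of continuous use, so exposure goes on between visits.

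**Working it through.** The plan has no figure to reproduce here, and no power or sample-size calculation bears on the point. The check is to set the sections side by side.

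**Step 1: the triggers in H1.** There are two, joined by *or*: discomfort, and excessive pressure. Either one is enough. Each is something felt, so two of two depend on sensation and none is a visible sign.

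**Step 2: whether sensation may be absent.** F1 selects for ulcer risk and does not exclude neuropathy. F2 measures neuropathy, and G2 uses its severity as an explanatory variable, which has a purpose only if some participants have it. The documents do not say how many.

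**Step 3: what could detect a painless lesion, by time.**

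| Time from device issue | Stated in the documents | Could it find an unfelt lesion? |
|---|---|---|
| Day 0 (Visit 1) | Dermatological exam; pressure with and without the insole; shoe fit | Sets the baseline and lowers risk; comes before home use |
| About 48 hours (Visit 2) | Adverse event check; edema measurement (Section D) | Probably, if the foot is bared and looked at; inspection is not named |
| About day 7 (Visit 3) | As above; Day 0 assessments may be repeated | Probably, on the same condition |
| About day 7 to day 28 | No visit listed | Relies on participant report |
| About day 28 (Visit 4) | Assessments similar to Day 0 | Yes, if the skin exam is among those repeated |
| No set time | Photographs and thermal images | Yes, but only when taken and reviewed |

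**Step 4: the length of the uncovered period.** 28 − 7 = 21 days, and 21 / 28 = 75% of the device period. Over these days the only stated participant trigger is the one in Step 1. The contact about three months after Visit 4 asks about ulcers, but the device has been returned by then.

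**Step 5: the number of delayed detections.** This would need the share of participants without protective sensation and the ulcer rate under the insole. The documents give neither, so no estimate is made.

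**The case against.** The strongest reply is that H1 is not the place where participants are instructed. It is an ethics form field that asks for risks to be described, filled with wording that reads as if written for participants. The consent form was not available for review (Section Q shows only its name). The content of the device education, Foot Questionnaire, Contact Agreement and follow-up questionnaire is not shown either. Any of these may already tell participants to look at their feet. This stands as a limit on confidence, and it is why the fix is conditional. It does not remove the point: H1 is participant-facing wording, it is in the documents, and it omits visible signs directly after naming ulcers.

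A reader might infer three stronger things, and the documents support none of them.
- *That there is no safety check before 4 weeks.* Adverse events are assessed at both early visits, and a new ulcer is an event that H1 itself anticipates.
- *That feet are not inspected at 48 hours and 1 week because the F2 visit lists name no inspection.* Those lists also leave out the edema measurement that Section D schedules at both visits. They are therefore not exhaustive, and absence from them is weak evidence. Measuring edema would normally expose the foot.
- *That only felt symptoms may be reported.* H1 says it is important to report them; it does not restrict reporting to them.

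It can also be said that an inspection at Visits 2 and 3 adds nothing between day 7 and day 28. That is correct. Only the daily look acts in that window, so it is the main fix and the inspection is secondary.

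**Conclusion.** The point holds as a mismatch between a named harm and the way participants are told to recognise it. H1 foresees foot ulcers, and both of its triggers need sensation, in a trial where loss of sensation is expected and not excluded. The safeguards at visits are real, but they leave about 21 of 28 days in which the visible text depends on the participant noticing something.

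This is a worthwhile safety improvement in a four-week pilot; it does not show that the design is unsound. Confidence is moderate. The conclusion rests on two assumptions: that some enrolled participants lack protective sensation, which the eligibility criteria and planned analyses imply, and that the unseen consent and education text does not already ask for a daily foot check. If it does, what remains is a wording mismatch in H1. The number of lesions that would be found earlier cannot be stated from these documents.

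**What to change.** **Main change.** In H1 and the device education, add an instruction along these lines: *Look at both feet every day, or have a carer do so. Stop using the insole and call us if you see redness, a blister or a break in the skin, or if you feel discomfort or excessive pressure.* If the consent form or device education already says this, align H1 with it. If the consent form carries the present H1 text, revise it too.

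**Minor addition.** In F2, make a shoes-off look at both feet part of the adverse event check at Visits 2 and 3, done while the foot is bare for the edema measurement.

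**Cost.** Revised wording, a few minutes per visit, and some extra calls about minor redness. No new visit or equipment is needed. The protocol does not say who does the adverse event check, so the site should make sure that this person can recognise early skin damage. The change lowers the risk of late detection but does not remove it.
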